## 3.5 Rationale for Study Design

#### 3.5.1 Why no Randomization?

In the proposed project, individuals will contact our mobile team after learning about the opportunity to begin a rapid induction with buprenorphine/naloxone. As described in more detail later, awareness of the intervention will precede contact with the research team via social media, targeted advertisement, and word of mouth. This is an important feature of the research since we want to be able to measure the acceptability and demand for such a strategy. We believe that it would not be ethical to randomly assign individuals at this point to an alternative treatment option that would require additional time and referral to a different location to initiate screening and intervention. As an "open label" trial, any randomization process would also become widely known among potential participants and contaminate the perception of the mobile team as able to reliably initiate rapid treatment engagement.

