  - Non-Medical and Other Services Form (NSMOS): This questionnaire was adapted from the Treatment Services Review (McLellan et al., 1992; Cacciola et al., 2008) for patients receiving substance abuse treatment. It is designed to capture all medical and social services received by the participant between study visits. The NSMOS counts substance abuse treatment, medical services, employment visits, legal services, family services and psychological/emotional. It takes 5 to 10 minutes to complete. The Non-Medical and Other Services Form (NSMOS) will be used to collect information from participants on

their healthcare utilization. This information will enable us to estimate costs incurred by the City of Philadelphia's Department of Public Health. Participants will be asked about the medical services and other relevant resources they have utilized between assessments. More specifically, participants will be asked about: visits and number of visits to an emergency room (not admitted to hospital); admittances (number and duration) to hospitals to detoxify from drugs or alcohol, or for other reasons; participation and number of days in outpatient treatment program for drug or alcohol problems; admittance (number and duration) in a residential program to detoxify or for other services; receipt, type, and prescribed dose, of medication to treat alcohol use disorder, opioid use disorder, or mental health disorder; care (number of times) received by a psychiatrist or psychologist, counselor or social worker; number of visits to a medical office and number of visits with a doctor; amount spent out of pocket on healthcare (including prescriptions); and coverage and type of health insurance. Study staff will administer this form at each assessment. Time to complete will vary by participant.

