## Comparison group – Treatment as usual

During the same period of time, participants will also be recruited at the City of Philadelphia Behavioral Health System Behavioral Assessment Centers (BAC) and Crisis Response Centers (CRC) located at Episcopal Hospital serving Kensington area and Hall Mercer BAC/CRC (a University of Pennsylvania program) serving South Philadelphia area. Two research assistants from the TRI-PHMC will enroll and follow-up 125 participants at BAC/CRC. The participants will complete the same assessments at baseline, 1- and 6-month follow-up. Authorization for the Philadelphia Department of Public Health to look shared information about their subsequent use of health department services (CARES database, http://www.phila.gov/hhs/data/Pages/Cares.aspx) will also be requested in the consent form. Research staff will only conduct assessments. Treatment engagement services will be provided by the staff of the BAC/CRC as usual.

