Analyses for Aim 3: We will estimate the total costs and per-participant costs of rapid initiation of MAT for opioid treatment engagement and use a cost-offsets approach to determine the economic value of this novel strategy. A cost-offsets approach requires a comparison of the total cost of the intervention (proposed enhanced procedure or treatment as usual) to the future costs of healthcare utilization avoided (i.e., benefits) due to the intervention. Healthcare utilization and medical costs will be estimated before and after participants receive either rapid initiation of MAT for opioid treatment engagement or treatment as usual. Information on healthcare utilization will be collected from participants at each assessment when study-staff administer the Non-Medical and Other Services Form (NSMOS; detailed description in Instruments section). Medical costs associated with these treatments/services will be estimated using Medicaid data. Costs of the intervention will be collected by [name], using the Drug Abuse Treatment Cost Analysis Program (DATCAP; detailed description in instruments section). She will interview staff in order to collect information on economic resource and cost variables such as staff salaries and benefits, study supplies and materials, major equipment, contracted services. building and facilities, and miscellaneous resources and costs. Recognizing that full-time staff members may devote only part of their work time to the proposed study, she will conduct a time-in-motion study with relevant study staff in order to track their time devoted to this study. Adjustments will then be made to salaries and benefits to reflect appropriate compensation attributed to this study. Similar adjustments will be made to reflect the time that some equipment, buildings and facilities, and miscellaneous resources and costs are attributed to the proposed study.

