Differences in pre-post medical costs will be used as an estimate of the value of downstream costs avoided due to the intervention. We will compare these differences across groups for statistical significance. We hypothesize that the medical costs after the intervention will be significantly lower for the participants that receive rapid initiation of MAT for opioid treatment than for the participants that receive treatment as usual. The economic value of this novel intervention will be positive if the costs of this novel intervention are outweighed by the medical cost savings that result from participants obtaining long-term and consistent opioid treatment. The proposed intervention is expected to aid with this process. Therefore, we hypothesize that the cost of rapid initiation of MAT for opioid treatment will be outweighed by the resulting avoidance of healthcare utilization costs.

We conduct our cost analyses from the perspective of the City of Philadelphia Department of Public Health since they may decide to scale-up the proposed services for other Philadelphia residents at risk of substance use overdose. Thus, we focus on healthcare utilization costs avoided as benefits of the proposed services. We may extend our analysis later to use a societal perspective that would consider other economic costs, such as criminal justice costs, unemployment costs, and participant costs (e.g., travel, work time missed, childcare expenses, etc.). Inclusion of the economic costs avoided due to opioid use disorder treatment will make the economic value of the proposed intervention even more positive than it is hypothesized to be when considering only healthcare utilization costs avoided due to opioid use disorder treatment.

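### Aim 3 compares pre-post cost change between self-selected groups with no confounder adjustment specified, so the cost offset may be biased in an unknown direction

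*Combined protocol and SAP*

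**What the plan says.** All of the Aim 3 analysis text stands in Section 5.2, under Analyses for Aim 3.

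- **Estimand and reading.** "Differences in pre-post medical costs will be used as an estimate of the value of downstream costs avoided due to the intervention".
- **Test.** "We will compare these differences across groups for statistical significance". No model, covariate, stratum, cost distribution or significance level is given.
- **Data.** "Healthcare utilization and medical costs will be estimated before and after participants receive either rapid initiation of MAT" or usual care. The length of the period before treatment is not given. Utilisation comes from the NSMOS form, which Section 3.7 describes as "designed to capture all medical and social services received by the participant between study visits". At baseline there is no earlier study visit, so that description sets no look-back.
- **Allocation.** There is no randomisation. Section 3.5.1 says that "individuals will contact our mobile team after learning about the opportunity to begin a rapid induction with buprenorphine/naloxone". For usual care, "participants will also be recruited at the City of Philadelphia Behavioral Health System Behavioral Assessment Centers (BAC) and Crisis Response Centers (CRC"), the City's entry points for urgent and crisis assessment (Section 2.4).
- **Confounding.** The propensity paragraph in Section 5.2 accepts that the group effect may be confounded and puts a propensity-score quintile into the study's models without saying which. Aim 1 names the score explicitly. The Aim 2 ASI model takes it by reference to Aim 1. Aim 3 does not mention it, and the Study Summary ties it to the engagement model only. The listed covariates are age, race/ethnicity, gender, previous overdoses, previous treatments, opioid type and depression.

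**The concern.** The plan gives the Aim 3 contrast a causal reading, and Sections 3.8.2 and 5.2 say that the City may decide on scale-up from it. Yet the adjustment that the plan considers necessary for engagement is not carried over to cost.

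A change score protects against one form of imbalance: a fixed cost gap between groups that is the same before and after. It does not protect against groups whose costs would have changed differently without the intervention. There are two routes to that here. First, people who choose an outreach team may differ from people who present at an assessment or crisis centre in ways that affect the course of their costs. Second, one arm's baseline period may contain a temporary peak. Everyone is enrolled within 12 months of an overdose, but the entry routes differ, so the peak need not be equal in the two arms. The undefined baseline look-back adds to this, because a pre-post cost difference over unequal or unstated windows has no clear meaning under any estimator.

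**Working it through.** **The plan's own figure.** The only power statement concerns engagement: 125 per group, 25% vs 40%, 80% completers, correlation 0.3. One time point needs 152 per group (two-sided 5%, 80% power). The repeated-measures factor for two time points is (1 + 0.3)/2 = 0.65, and 152 × 0.65 = 98.8. Rounded up and inflated for 20% loss, 99/0.80 gives 124, against 125 stated. Power with 100 completers per group is 80.5%. The figure reproduces, and the Aim 3 point does not touch it. Aim 3 has no stated SD, sample size or power.

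**Set-up for cost (all inputs assumed unless a source is named).**
- n = 112 per group, from 125 × 0.90 (month-6 follow-up expected in Section 3.7).
- Pre-post correlation of cost: r = 0.3 to 0.7.
- Baseline gap, usual care above mobile: D = 0.1 to 0.5 SD.
- Fraction of the gap that remains afterwards: k.
- No true effect; two-sided 5%; costs treated as normal for simplicity.

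**Bias, mobile minus usual care.**
- Change score: (−kD) − (−D) = (1 − k)D.
- Baseline-cost adjustment: (−kD) − r(−D) = (r − k)D.

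A positive value makes mobile costs appear to fall less than usual-care costs, so it favours usual care. If the mobile arm had the higher baseline, every sign would reverse.

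**Change score when the gap fades to k = r.** Bias = (1 − r)D, and SE = √(2(1 − r)) × √(2/n).

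| r | D | Bias (SD) | SE | Rejection rate, no true effect |
|---|---|---|---|---|
| 0.7 | 0.1 | 0.03 | 0.104 | 6% |
| 0.7 | 0.2 | 0.06 | 0.104 | 9% |
| 0.5 | 0.3 | 0.15 | 0.134 | 20% |
| 0.3 | 0.5 | 0.35 | 0.158 | 60% |

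Over 100 to 125 per group and the same grid of r and D, the rates run from about 6% to 65%.

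**Neither estimator is safe under every pattern.** Simulated with r = 0.5, D = 0.3, n = 112 (4,000 to 5,000 runs per row):

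| Pattern of the gap | Change score: bias, rejection | Baseline-adjusted: bias, rejection |
|---|---|---|
| Stable (k = 1) | 0.00, 5.5% | −0.15, 24.2% |
| Fades to r (k = 0.5) | 0.15, 20.5% | 0.00, 4.9% |
| Vanishes (k = 0) | 0.30, 61% | 0.15, 25% |

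The biases match the formulas: for example (0.5 − 1) × 0.3 = −0.15 and (0.5 − 0) × 0.3 = 0.15. The middle row is the one pattern in which baseline adjustment is exactly unbiased, so it should not be used alone to argue for that method.

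**The case against.** The strongest reply is that the propensity paragraph precedes all the aim-specific analyses, is headed as the answer to non-randomised allocation, and does not limit the quintile to any aim. A reader might infer from Aim 3's silence that the cost comparison is deliberately raw. The documents do not support that: they never say it is unadjusted. What stands is an ambiguity. Aim 3 names no model in which a stratum could sit, and the Study Summary attaches the score to engagement alone. Even if the quintile does apply, no prior cost or utilisation is listed among its covariates, although that list is introduced as inclusive rather than closed.

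A reader might also infer that the cost offset is confounded, or inflated in favour of the mobile team. Neither is shown. Differencing already removes stable additive gaps. Both arms enrol when people seek treatment, and both require a recent overdose. Only the CRCs are crisis services; the BACs give urgent assessments in working hours. The documents contain no cost data to show that usual-care costs would fall. If a crisis peak did exist, it would work against the mobile arm and the plan's own hypothesis. Moreover, Aim 3 treats usual care as an intervention with its own cost, so the index BAC/CRC contact can be read as lying outside the pre-period. That reading is reasonable but is not stated.

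Finally, replacing the change score by baseline-cost adjustment may look like the obvious cure. The second table shows that it only exchanges one untestable assumption for another.

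**Conclusion.** The point holds in a limited form. For a contrast that the plan reads causally, between groups that it accepts may be confounded, no propensity stratum or other confounder adjustment is specified. The general propensity sentence leaves it unclear whether Aim 3 is covered, no prior cost or utilisation is among the named covariates, and the baseline cost window is undefined. The estimated cost offset may therefore be biased, in a direction that cannot be told from the documents.

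The bias of 0.03 to 0.35 SD and the rejection rates of about 6% to 65% are illustrations. They rest on assumed r and D, on normal costs, and on a gap that fades exactly to r. With a stable gap the change score has no bias; with a gap that vanishes completely the bias is the whole of D. The figures should not be quoted as the error rate of this trial.

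This is a secondary economic aim. The primary endpoint and its power are unaffected. It should still be corrected before analysis, because the result may inform a scale-up decision and the main remedy uses a variable that is already being built.

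**What to change.** 1. State that the propensity quintile applies to Aim 3, and estimate the group difference in cost change in a regression that includes it.
2. Add baseline utilisation or cost to the propensity model.
3. Use a bootstrap interval for the mean difference, or another skew-tolerant method that allows zero costs. A standard gamma model does not take zeros.
4. Report the change-score result together with a baseline-cost-adjusted result as a sensitivity analysis, and say under which pattern of baseline gap each is unbiased.
5. Define equal windows: set the NSMOS baseline look-back to match the 6-month post period.
6. Support the look-back with CARES records where consent covers them. Sections 3.2 and 3.8.1 describe records from before and after enrolment, whereas Section 4.8.2 and the Treatment as usual text describe later use only. Reconcile these passages first. CARES is described as service utilisation, so costs would still have to be attached, as Aim 3 already plans to do with Medicaid data.
7. State that the index BAC/CRC contact is counted as usual-care cost and not as pre-period cost.

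The cost is analysis wording, a little programming, and a defined recall period on an existing form. The recall period changes data collection slightly, so it needs to be set before baseline interviews, or applied from CARES if they have already been done.

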#### Rapid initiation of BUP/NX Version 1: Nov-15-2018

months. More than 90% of those who remained in treatment at 12 months were opiate-abstinent (Bachhuber, Thompson et al. 2018). Importantly, and in contrast to many other programs in the City, the STEP program has a waiting list of nearly 200 individuals.

The proposed project incorporates the concept of rapid initiation of MAT and consequently, the rapid control of withdrawal symptoms. A mobile team (Nurse Practitioner, Certified Peer Recovery Specialist, and a Case manager) will provide medication, counseling and treatment engagement support for one month. During this time, individuals will be linked to community MAT providers with unused capacity.

We will determine the economic value of the mobile intervention relative to treatment as usual from the perspective of the City of Philadelphia's Department of Public Health. [name], a Health Economist in the HIV Prevention Research Division, Department of Psychiatry, Perelman School of Medicine at the University of Pennsylvania, will lead this portion of study activities with consultations with colleagues at the Center for Health Economics of Treatment Interventions for Substance Use Disorder, HCV, and HIV (CHERISH). The results of this analysis will inform future policy decisions regarding implementation of this novel, mobile strategy for rapid initiation of MAT as a method for engagement in long-term evidence-based treatment. If the intervention in this study shows positive economic value, the City of Philadelphia's Department of Public Health may scale-up the intervention to reach more people throughout the city that may be at risk of opioid overdose. Enhanced interventions may require a greater amount of resources than alternative methods of more basic interventions or the usual standard of care. However, resource-intensive interventions may be justified through the achievement of better outcomes resulting from administering enhanced procedures.

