# 5.2 Sample Size and Power Determination

Our power analysis has been based on this primary aim. Our primary hypothesis is that participants who received rapid induction will more likely be engaged in ongoing treatment at 1- and 6-month follow-up than participants who sought treatment at BAC/CRC. We will test this hypothesis at a 5% level of significance. Our principal interest is in the comparison of engagement rates between the mobile intervention and BAC/CRC groups, at months 1 and 6. Preliminary data suggest an engagement rate of about 20-30% in the BAC/CRC group. Assuming a steady loss to attrition that yields 80% completers, and a within-subject correlation of 0.3, the methods of Diggle et al. (Diggle, Heagerty et al. 2002) show that our sample size of 125 in each group yields 80% power for differences of about 15% in engagement rates between the two groups (e.g., 80% power for BAC/CRC: 25% vs. Mobile: 40%, corresponding to a RR=1.6 and an OR=2.0)

**Propensity score model to account for non-randomized allocation:** The participants are not randomly assigned to the mobile rapid induction intervention and BAC/CRC groups, so it is possible that there will be confounding of the group effect with the effects of characteristics of the participants. We will use a propensity score approach (Rosenbaum 2002, Rothman, Greenland et al. 2008) to account for this. We will use a broad range of baseline variables as covariates in a logistic regression model predicting treatment group, including age, race/ethnicity, gender, number of previous overdoses, number of previous treatments for opiate use disorder, type of opioid used, and depression. The model will yield predicted probabilities of BAC/CRC group for all participants (the propensity score), and we will create a five-level ordinal variable based on the quintiles of the propensity score. We will then include this ordinal variable as a stratum variable in our models.

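### Aim 3 tests whether medical savings differ from zero, but its conclusion is that savings exceed program cost, and no interval or test is planned for that net comparison

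*Combined protocol and SAP*

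**What the plan says.** The analyses for Aim 3 in section 5.2 take the change in medical costs as the measure of savings: "Differences in pre-post medical costs will be used as an estimate of the value of downstream costs avoided due to the intervention". The inferential step follows: "We will compare these differences across groups for statistical significance". The matching hypothesis concerns medical costs only: "We hypothesize that the medical costs after the intervention will be significantly lower for the participants that receive rapid initiation of MAT".

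The plan then moves to a net claim. It states that "The economic value of this novel intervention will be positive if the costs of this novel intervention are outweighed by the medical cost savings", and adds that "we hypothesize that the cost of rapid initiation of MAT for opioid treatment will be outweighed by the resulting avoidance of healthcare utilization costs". Program costs come from DATCAP and a time-in-motion study of staff.

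No confidence interval, test, bootstrap or sensitivity analysis is given for savings minus program cost, either here or where the economic evaluation is described in sections 3.1, 3.7 and 3.8.2. The 5% level in section 5.2 is attached to the primary engagement hypothesis.

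Sections 3.1 and 3.8.2 name the use of the result: "If the intervention in this study shows positive economic value, the City of Philadelphia's Department of Public Health may scale-up the intervention".

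**The concern.** Whether savings differ from zero and whether savings exceed program cost are two hypotheses with different nulls. The plan provides inference for the first and concludes on the second. A saving can be clearly above zero and still fall short of what the program costs, so a significant medical-cost result could be misread as evidence of net value. In the other direction, an estimated saving can exceed program cost by chance alone, and nothing in the plan would tell the reader how likely that is.

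The result is meant for a budget-holder. If the City is told that economic value is positive, it needs to know how firmly the data support that statement.

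**Working it through.** **The plan's own figures.** Aim 3 has no SD, program cost, margin, alpha or power to reproduce. The one power figure, for the primary aim, does reproduce. For 25% vs 40% at two-sided 5%, 152 per group are needed at a single time point. The two-visit factor is (1 + 0.3)/2 = 0.65, so 152 × 0.65 = 98.8 completers, or 124 per group after 20% loss, against the planned 125. That calculation does not bear on Aim 3.

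**Setup.** Let S be the true saving per participant (the between-group difference in pre-post medical cost change), C the incremental program cost, treated as known, and SE the standard error of the estimated saving. The estimate is taken as approximately normal and unbiased.

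- Planned test: null S = 0.
- Stated conclusion: S > C.
- Net value read from estimates alone: P(estimate > C) = 1 − Φ((C − S)/SE).

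**Results that need no dollar assumption.**

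- At break-even (S = C): 1 − Φ(0) = 50%.
- At a true loss of 0.25, 0.5 or 1 SE: 40%, 31%, 16%.
- The test against zero, with true net value zero, is significant 17%, 50%, 85% and 98% of the time when C is 1, 1.96, 3 and 4 SE. It therefore says little about net value.
- If the lower two-sided 95% bound of the net saving had to exceed zero, the rate at break-even would be 2.5%.

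A simulation with skewed (lognormal) costs, 100 per group and 20,000 runs, with saving and program cost both $3,000, agrees: 49.3% from estimates alone and 1.9% with the interval.

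**Dollar illustration.** Assumed: SD of the cost change of $10,000, $20,000 or $30,000. From section 3.7: 90% follow-up at month 6, so 0.90 × 125 ≈ 112 per group. SE = SD × √(2/112). The true loss is set at $1,000 per participant (S = C − $1,000).

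The last two columns take the other possible reading, in which significance against zero is also required. The estimate must then exceed the larger of C and 1.96 SE.

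| SD | SE | Estimates alone | Significance also required, C = $4,000 | Significance also required, C = $2,000 |
|---|---|---|---|---|
| $10,000 | $1,336 | 23% | 23% | 11% |
| $20,000 | $2,673 | 35% | 20% | 6% |
| $30,000 | $4,009 | 40% | 11% | 4% |

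Example for the first row of the estimates-alone column: 1 − Φ(1,000/1,336) = 0.227.

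With the 80% completers assumed in section 5.2 (100 per group), the estimates-alone rates are 24%, 36% and 43% at SDs of $10,000, $20,000 and $40,000.

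**Significant savings without net savings.** At an SD of $10,000, any estimated saving above 1.96 × $1,336 = $2,619 is significant against zero. An estimated saving of $3,000 would be significant, yet it would be $1,000 short of a program cost of $4,000.

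**The case against.** The sentence on positive economic value can be read as defining the quantity of interest. It mentions neither point estimates nor a declaration. That is fair: the point-estimate rule is inferred from the absence of any other. But the net claim is also put forward as a hypothesis, and a hypothesis with no planned inference is a gap on either reading.

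The significance comparison comes earlier in the same paragraph and might be intended as a precondition. The text neither says so nor excludes it. If it is, the error rates fall when program cost is below about 1.96 SE, as the table shows. Above that it adds nothing, and at break-even the rate is again 50%. So a reader who infers that the plan has no error control at all goes too far.

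The 50% figure holds for any unbiased, symmetric estimator at exact break-even, where nothing is lost. Under this model a truly losing program appears favourable less than half the time, so a reader should not infer that it would probably be declared cost-saving.

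Nor is positive value an automatic trigger. The wording on scale-up is permissive, and sections 3.1 and 3.8.2 also allow that better outcomes may justify a resource-intensive intervention.

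Aim 3 is also unpowered. With 100 per group and an SD of $10,000 to $20,000, 80% power for an interval excluding a net loss needs a true net benefit of about $3,960 to $7,920 per participant. That argues against making such an interval a pass/fail rule for the aim. It does not argue against reporting the interval.

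**Conclusion.** The concern holds: the one planned comparison addresses savings against zero, the stated conclusion is savings above program cost, and the uncertainty of the net figure is left unaddressed. This is a mismatch between analysis and conclusion, not a sample-size error.

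The break-even rate of about 50% depends only on an approximately symmetric, unbiased estimate read without an interval. The 23% to 40% range depends on the assumed SDs, 112 per group, a $1,000 loss and a program cost treated as fixed. It would be lower if significance were required and program cost were small relative to the SE. Since the documents supply neither a cost SD nor a program cost, the actual size cannot be fixed from them.

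**What to change.** In the analyses for Aim 3 in section 5.2:

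- Define the estimand as net cost per participant: (mobile minus treatment-as-usual program cost) plus (mobile minus treatment-as-usual change in medical cost, post minus pre). A negative value is a saving. This also settles whether program cost means total or incremental cost.
- Adjust for the propensity strata of section 5.2, because the groups are not randomized.
- Report a 95% bootstrap interval, resampling participants and refitting the propensity score in each resample.
- Vary the DATCAP program cost in a sensitivity analysis, because resampling participants does not capture its uncertainty.
- Base any statement of positive economic value on the net estimate and its interval, and do not describe the intervention as shown to be cost-saving when the interval includes a net loss.
- Keep the test of savings against zero as supportive.

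The cost is about a paragraph of text and a little more analysis, and a claim of positive value becomes harder to make. One item needs confirming: usual engagement services are delivered by BAC/CRC staff (section 4.9.1), while the time tracking is described for study staff, so the plan should state how program cost in the comparison group will be captured.
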